2.2 Hypotheses and/or Estimations

The study is descriptive in nature without a comparator arm, and as such no formal statistical hypothesis is defined.

[figure not shown]
3. Study Overview

3.1 Study Design

Study 20190389 is a phase 4 open-label study that will enroll subjects with EM or CM in an approximately 1:1 ratio. The study will comprise the following periods:

- A combined screening/baseline period consisting of the following:
 - A screening visit (which may coincide with the first day of the baseline period) for the assessment of eligibility criteria
 - A baseline period of approximately 4 weeks (no less than 28 days; up to 35 days) to collect data on migraine headaches and acute headache medication use using electronic diary (eDiary) and to assess compliance in eDiary usage
- A 24-week open-label treatment period

Eligible subjects may enter the baseline period at the same visit or may delay baseline procedures up to 3 weeks after the screening visit. At completion of the baseline period, those who meet eligibility criteria and choose to proceed will be enrolled and will enter the open-label treatment period to receive erenumab 70 or 140 mg once every 4 weeks (Q4W) by subcutaneous (SC). All subjects will be started on a 70 mg dose of erenumab at day 1 with provider discretion for dose optimization (either 70 mg or 140 mg), which is recommended to be completed by week 12. All subjects will be required to enter the study on 1 standard of care preventive medication for their migraine, whose dose then can be adjusted by the investigator's discretion and must be stable by week 12. The treating clinician and a key family member (if available) for each participating subject will be invited to complete an mGI-I at weeks 12, 16, 20, and 24/End of Study (EOS) for the mGI-I endpoints.

Figure 1 1. Study Schema

* All subjects will be started on a 70 mg dose of erenumab at day 1 with provider discretion for dose optimization. Dose optimization will allow patients to remain on 70 mg, increase the dose from 70 mg to 140 mg, and if needed decrease the dose back down from 140 mg to 70 mg. It is highly recommended that all erenumab dose adjustments be completed by week 12, after which all subjects should remain on the week 12 erenumab dose for the rest of the study. Additional dose adjustments after week 12 are not recommended and must only be made if deemed medically necessary by the investigator.

** Baseline may begin on the same day as screening

3.2 Sample Size

The total sample size of approximately 322 subjects (effective sample size of 289, assuming 10% dropout at week 24) is driven by the precision of the proportion estimates for the binary secondary endpoints, which targets a half-width of 95% confidence intervals (CIs) around 5%. The half-width of the 95% CI will be the widest when the estimated percentage is 50%, given a fixed sample size, and will become narrower if the percentage moves further away from 50% (see [Table 3-1](#)).

Table 3-1. Half-width of 95% CI for Various Estimated Percentages With Effective Sample Size of 289 Subjects

Percentage Estimate	Half-width of 95% CI With Effective Sample Size = 289
50%	5.8%
60%	5.6%
70%	5.3%
80%	4.6%

Given the evolving landscape of migraine preventive trials and treatment paradigm, the exploratory design of this trial, and the descriptive nature of the study objectives and endpoints, it had been understood that prolonging screening and enrollment efforts beyond this point would be of little additional value, thus, it has been decided to terminate study 20190389 early to enroll only 240 subjects.

[Table 3-2](#) is the updated half-width of 95% CI based on the sample size of 240 subjects (effective sample size of 216, assuming 10% dropout at week 24).

Table 3-2. Half-width of 95% CI for Various Estimated Percentages With Effective Sample Size of 216 Subjects

Percentage Estimate	Half-width of 95% CI With Effective Sample Size = 216
50%	6.7%
60%	6.5%
70%	6.1%
80%	5.3%

3.3 Adaptive Design

The adaptive design is not applicable for this study.

4. Covariates and Subgroups

4.1 Planned Covariates

All model-adjusted analyses of primary and secondary efficacy endpoints will include the corresponding baseline value for the endpoint being analyzed **if applicable**, visit, the prevailing erenumab dose from week 12 onwards, and baseline MMD in the model.

4.2 Subgroups

The primary and secondary endpoints will be analyzed in the following subgroups:

- Whether remained on standard of care migraine preventive treatment throughout the study (yes vs no)
- Migraine type (EM vs CM) based **on both CRF data collected on form “Headache and Migraine Frequency Medical History” during screening and eDiary collection during baseline**

The subgroups will be re-examined for appropriateness and may be re-categorized (due to small sample size, for example, if there are < 10% of subjects within a subgroup) before final analysis.

5. Definitions

5.1 Definition of Terms Included in Study Endpoints

5.1.1 Efficacy Endpoints Based on Monthly Collection

The daily eDiary collection will occur during the baseline period and months 4, 5, and 6.

Subjects' daily headache information will be collected through the following questions.

Possible outcomes on migraine-related endpoints are summarized below:

Table 5-1. Definitions of Migraine Day, Headache Day, and Acute Migraine-specific Medication Day

	Scenarios									
	1	2	3	4	5	6	7	8	9	10
eDiary data collection										
Headache (Y/N)	Yes	Yes	Yes	Yes	Yes	Yes	No	No	No	No
If Y, (a) Pain intensity (1 to 10)	1 to 10	1 to 10	1 to 10	1 to 10	1 to 10	1 to 10	NA	NA	NA	NA
(b) Migraine (Y/N)	Yes	Yes	Yes	No	No	No	NA	NA	NA	NA
(c) Acute medication for headache (Y/N)	Yes	Yes	No	Yes	Yes	No	NA	NA	NA	NA
If Y, Triptan (Y/N)	Yes	No	NA	Yes	No	NA	NA	NA	NA	NA
If N, Aura (Y/N)	NA	NA	NA	NA	NA	NA	Yes	Yes	Yes	No
If Y, acute medication for aura (Y/N)	NA	NA	NA	NA	NA	NA	Yes	Yes	No	NA
If Y, Triptan (Y/N)	NA	NA	NA	NA	NA	NA	Yes	No	NA	NA
Endpoint definition										
Headache Day	Yes	Yes	Yes	Yes	Yes	Yes	Yes	No	No	No
Migraine Day	Yes	Yes	Yes	Yes	No	No	Yes	No	No	No
Acute Migraine-specific Medication Day	Yes	No	No	Yes	No	No	Yes	No	No	No

Migraine Type

CM is defined as subjects with ≥ 15 headache days per month of which ≥ 8 headache days meet criteria as migraine on either CRF data collected on form “Headache and Migraine Frequency Medical History” during screening or eDiary collection during baseline; **EM** is defined as subjects who does not fulfill criteria for **CM**.

Diary Day

A calendar day (00:00 to 23:59) with complete migraine headache, aura, and acute migraine headache medication data recorded in the eDiary device

Headache Day

A calendar day (00:00 to 23:59) in which the subject reports a headache (ie, Scenarios 1 to 7 in [Table 5-1](#))

Migraine Day

A calendar day (00:00 to 23:59) in which the subject reports a migraine (ie, Scenarios 1 to 4 in [Table 5-1](#)) or takes a migraine-specific medication (ie, Scenario 7 in [Table 5-1](#))

Acute Migraine-specific Medication Day

A calendar day (00:00 to 23:59) in which the subject takes a migraine-specific medication (ie, Scenarios 1, 4, and 7 in [Table 5-1](#)).

Monthly Frequency Variable in Days

Number of days of interest during one monthly interval as defined in [Table 5-2](#). Monthly frequency variables include

- Monthly Migraine Days (MMD)
- Monthly Acute Migraine-specific Medication Days

The following proration rule will be applied to all monthly frequency variables for each monthly interval.

Within Each Monthly Interval	Monthly Frequency Variable
≥ 14 diary days	Prorate to 28-day equivalent without rounding $\frac{\text{Number of frequency days within each monthly interval}}{\text{Number of diary days within each monthly interval}} * 28$
< 14 diary days	Set to missing

5.1.2 Efficacy Endpoints Based on Clinical Outcome Assessments

- **Treatment Satisfaction Questionnaire for Medication (TSQM)**

The Treatment Satisfaction Questionnaire for Medication (TSQM) version 1.4 is a 14-item instrument designed to measure important dimensions of patients' experiences with their medication. It has 4 domains: effectiveness, side effects, convenience, and global satisfaction. Scores range from 0 to 100, with higher scores indicating greater satisfaction. The recall period is the last two to three weeks, or since the medication was last used.

Scoring Algorithm: TSQM Scale scores range from 0 to 100 and no computed score should be lower or higher than these limits.

Effectiveness: Effectiveness domain contains Item 1 to Item 3

$$\text{Effectiveness} = \frac{[(\text{Item 1} + \text{Item 2} + \text{Item 3}) - 3]}{18} \times 100$$

Side Effects: Side effects domain contains Item 5 to Item 8

$$\text{Side Effects} = \frac{[(\text{Item 5} + \text{Item 6} + \text{Item 7} + \text{Item 8}) - 4]}{16} \times 100$$

Convenience: Convenience contains Item 9 to Item 11

$$\text{Convenience} = \frac{[(\text{Item 9} + \text{Item 10} + \text{Item 11}) - 3]}{18} \times 100$$

Overall satisfaction: Overall satisfaction domain contains Item 12 to Item 14

First recode Item14, recode Item 14 = (Item14 - 1) × 5/6

Then

$$\text{Overall satisfaction} = \frac{[(\text{Item 12} + \text{Item 13} + \text{Item 14}) - 3]}{12} \times 100$$

- **Migraine Global Impression Item (mGI-I)**

The mGI-I is a single item instrument designed to measure improvement/worsening in migraine. The 3 versions of the instrument include the perspective of study subjects, key family members, and treating clinicians measured on the following scale: much improved; a little improved; no change; a little worse; or much worse. The recall period is the past 7 days.

- **Migraine Functional Impact Questionnaire (MFIQ)**

The Migraine Functional Impact Questionnaire (MFIQ) version 2.0 is a self-administered 26-item instrument measuring the impact of migraine on broader functioning including 4 domains: Impact on Physical Functioning (items 1 to 5), Impact on Usual Activities (items 6 to 15), Impact on Social Functioning (items 17 to 21), and Impact on Emotional Functioning (items 22 to 26). In addition, there is 1 stand-alone global item (item 16) assessing the overall impact on usual activities. Subjects respond to each item using a 5-point scale assigned scores from 1 to 5, with 5 representing the greatest burden. Each domain score will be calculated as the sum of the item responses (ie, raw score) and rescaled to a 0-100 scale according to the formula below, with higher scores representing greater burden. No total score is created for the MFIQ. The recall period is the past 7 days.

$$\text{Domain Score} = \frac{(\text{Raw score} - \text{Lowest possible raw score})}{(\text{Highest possible raw score} - \text{Lowest possible raw score})} * 100$$

For the purposes of domain scoring, “does not apply” will be imputed with the mean of other items in the domain.

- **Migraine Symptom Severity Scale (MSSS)**

The Migraine Symptom Severity Scale (MSSS) is a 7-item questionnaire that assesses frequency of pain and other symptoms associated with migraines. Responses are as follows: “never”, “rarely”, “less than half the time”, “half the time or more”, and “all or nearly all of the time”. The responses are given a value from 1 to 3 as follows: Never = 0, Rarely = 1, Less Than Half the Time = 2, Half the Time or More = 3, and All or Nearly All of the time = 3. The MSSS score is the sum of the 7 items, and has a range from 0 to 21.

- **Migraine Interictal Burden Scale (MIBS-4)**

The Migraine Interictal Burden Scale (MIBS-4) measures interictal migraine-related burden with 4 questions that assess impairment in work or school, impairment in family

and social life, difficulty making plans or commitments, and emotional/affective and cognitive distress. Each of the 4 questions is responded to using 1 of 6 response categories: "Don't know/NA" (Score = 0), "Never" (Score = 0), "Rarely" (Score = 1), "Some of the time" (Score = 2), "Much of the time" (Score = 3) or "Most or all of the time" (Score = 3). Each question is multiplied with its score and summed up to produce total score ranges from 0 to 12. The MIBS-4 total scores are categorized into 4 level of interictal burden: None (0), Mild (1 to 2), Moderate (3 to 4) and Severe (5 or higher).

Total Score = {[(Number of responses for 'Don't Know' for Item 1 to Item 4)* 0] +
[(Number of responses for 'Never' for Item 1 to Item 4)* 0] +
[(Number of responses for 'Rarely' for Item 1 to Item 4)* 1] +
[(Number of responses for 'Some of the time' for Item 1 to Item 4)* 2] +
[(Number of responses for 'Much of the time' for Item 1 to Item 4)* 3] +
[(Number of responses for 'Most or all of the time' for Item 1 to Item 4)* 3]}

- **Generalized Anxiety Disorder Scale (GAD-7)**

The Generalized Anxiety Disorder Scale (GAD-7) is a self-administered 7-item instrument that uses some of the Diagnostic and Statistical Manual (of Mental Disorders) fifth edition (DSM-V) criteria for general anxiety disorder (GAD) to identify probable cases of GAD along with measuring anxiety symptom severity. Responders are asked to rate the frequency of anxiety symptoms in the last 2 weeks on a Likert scale ranging from 0 (not at all) to 3 (nearly every day). Items are summed to provide a total score. Score interpretation is as follows: 1 to 4 minimal symptoms, 5 to 9 mild symptoms, 10 to 14 moderate symptoms, and 15 to 21 severe symptoms. Changes of 5 points or more are clinically meaningful.

- **Patient Health Questionnaire (PHQ-9)**

The Patient Health Questionnaire (PHQ-9) is a self-administered questionnaire, widely used for diagnosis and severity assessment of depression in primary care settings. The Patient Health Questionnaire (PHQ) is a 9-question, self-administered instrument for screening, diagnosing, monitoring, and measuring the severity of depression. It incorporates Diagnostic and Statistical Manual (of Mental Disorders) fourth edition (DSM-IV) depression diagnostic criteria with other leading major depressive symptoms into a brief self-report tool. The tool rates the frequency of the symptoms which factors into the scoring severity index. PHQ-9 scores each of the 9 DSM-IV criteria as "0" (not

at all) to “3” (nearly every day). The score is calculated as the sum of the item responses and corresponds to one of the 5 severity categories: Minimal or None = 0 to 4, Mild = 5 to 9, Moderate = 10 to 14, Moderately Severe = 15 to 19, and Severe = 20 to 27. Question 9 on the PHQ-9 screens for the presence and duration of suicide ideation.

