8.3 Efficacy Assessments

8.3.1 Treatment Satisfaction Questionnaire for Medication

The TSQM version 1.4 is a 14-item instrument designed to measure important dimensions of patients' experiences with their medication. It has 4 domains: effectiveness, side effects, convenience, and global satisfaction. Scores range from 0 to 100 with higher scores indicating greater satisfaction. The recall period is the last 2 to 3 weeks, or since the medication was last used.

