
Change from baseline in subject functional impairment domain score at week 24, as measured by the Migraine Functional Impact Questionnaire (MFIQ)
 
 – Physical function domain score – Usual activities domain score – Emotional function domain score – Social function domain score 	
1. Summary statistics using observed data (after intercurrent event handling);
 
2. The change from baseline in subject functional impairment domain score at week 24, as measured by the MFIQ will be analyzed using a generalized linear mixed effects model with the identity link function. The model will include baseline subject functional impairment domain score, visit, the prevailing erenumab dose from Week 12 onwards, and baseline MMD based on observed data. The mean change from baseline in subject functional impairment domain score at week 24 with the corresponding 95% CI will be estimated from the LSM of the mixed effects model, and p-values comparing with zero at a two-sided 5% significance level will be reported.

Endpoint	Primary Summary and Analysis Method
	
3. The efficacy analysis set will be used for this endpoint analysis.
 
4. This endpoint will be analyzed separately for each functional domain.

Table 9-3. Exploratory Efficacy Endpoint Summary Table

Endpoint	Primary Summary and Analysis Method
Change from baseline in TSQM overall satisfaction scale score at weeks 12, 16, and 20 and mean over weeks 16, 20, and 24	This endpoint will be analyzed same as primary efficacy endpoint.
Achievement of overall satisfaction as defined by subject reporting of satisfied, very satisfied, or extremely satisfied on item 14 of the TSQM version 1.4 at weeks 12, 16, and 20.	This endpoint will be analyzed same as primary efficacy endpoint.
Change from baseline in TSQM sub-scale domain scores at weeks 12, 16, 20 and 24 and mean over weeks 16, 20, and 24: – effectiveness – side effects – convenience	This endpoint will be analyzed same as primary efficacy endpoint. Note: Use baseline value covariate as a “Baseline TSQM sub-scale domain score”
Improvement in subject global impression at weeks 12, 16, and 20, as defined by subject reporting of much improved or a little improved on the mGI-I Improvement in treating clinician's global impression at weeks 12, 16, and 20, as defined by treating	This endpoint will be analyzed same as above mentioned mGI-I endpoint.

Endpoint	Primary Summary and Analysis Method

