9.5.1 Analyses of Primary Efficacy Endpoint(s)/Estimand(s)

The primary endpoint, the change from baseline in the TSQM overall satisfaction scale score at week 24, as measured by items 12 to 14 of the TSQM version 1.4 will be analyzed using a repeated measures mixed effects model, including baseline TSQM overall satisfaction scale score, visit, the prevailing erenumab dose from Week 12 onwards, and baseline MMD **based on observed data**.

The mean change from baseline in TSQM overall satisfaction scale score at week 24 will be estimated from the least-squares mean (LSM) of the mixed effects model, and the corresponding 95% CI will be provided. The nominal p-value will be reported by comparing the mean change from baseline in TSQM overall satisfaction scale score at week 24 to zero with a two-sided 5% significance level.

This endpoint will be analyzed using the following subgroups **respectively**:

- Whether remained on standard of care migraine preventive throughout the study (yes vs. no)
- Migraine type (EM vs. CM)

The subgroups will be re-examined for appropriateness and may be re-categorized (due to small sample size, for example, if there are < 10% of subjects within a subgroup) before final analysis.

The purpose of the subgroup analyses is to explore if the treatment effect varies across subgroups of interest. Subgroup analyses will be performed using the same method as primary analysis method but within level of each subgroup of interest.

The efficacy analysis set will be used for this endpoint analysis.

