9.7 Other Analyses

Not applicable.

10. Changes From Protocol-specified Analyses

Frequency of headache and migraine days collected on CRF “Headache and Migraine Frequency Medical History” at screening period will be included to derive migraine type, in addition to eDiary at baseline.

The definition of efficacy analysis set stated in the protocol is not applicable to all efficacy endpoints and has been corrected in Section 6.3 to what was intended. These changes will also be documented in the clinical study report.

11. Literature Citations / References

NA

12. Prioritization of Analyses

Prioritization of analyses has not been identified at this time.

13. Data Not Covered by This Plan

There are no plans to specifically analyze or summarize the following substudy outcome variables.

- Migraine impact
- Treatment efficacy
- Migraine experience

Qualitative data on changes resulting from treatment received in the open-label treatment period will be collected via telephone interview.

Data will be analyzed to achieve the study objectives, using qualitative data analysis software (ie, ATLAS.ti).

14. Appendices

Not applicable.

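### The SAP's formula for the primary endpoint score (TSQM overall satisfaction) breaks the SAP's own 0 to 100 limit: the lowest answers score -8.33 if items are coded from 1

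*SAP*

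**What the plan says.** SAP 5.1.2 opens the TSQM scoring algorithm with a limit on all four domains: "TSQM Scale scores range from 0 to 100 and no computed score should be lower or higher than these limits". Protocol 8.3.1 gives the same range: "Scores range from 0 to 100 with higher scores indicating greater satisfaction".

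For the domain behind the primary endpoint, the SAP says "Overall satisfaction domain contains Item 12 to Item 14" and gives two steps. The first is "First recode Item14, recode Item 14 = (Item14 - 1) × 5/6". The second adds the three items, subtracts 3, divides by 12 and multiplies by 100. The protocol prints no formula.

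For the MFIQ, the same SAP section writes out its general rule. The raw sum is "rescaled to a 0-100 scale according to the formula below", which subtracts the lowest possible raw score and divides by the difference between the highest and lowest possible raw scores.

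**The concern.** The recode and the subtracted constant do not fit together. Subtracting 3 suits three items that each start at 1, but after the recode Item 14 starts at 0. The lowest possible sum is then 2, and the formula goes below the limit set in the same section.

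This score is the primary endpoint. It also enters the primary model as a covariate, a "repeated measures mixed effects model, including baseline TSQM overall satisfaction scale score" (SAP 9.5.1), and it supplies the exploratory results in SAP Table 9-3: "Change from baseline in TSQM overall satisfaction scale score at weeks 12, 16, and 20 and mean over weeks 16, 20, and 24". Under the composite strategy in SAP 9.1, the worst post-baseline value up to discontinuation of investigational product is also taken from it. The study is descriptive, so the estimated mean change and its confidence interval are the main result, and the scale of the score bears directly on both.

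The precision tables in SAP 3.2 are not affected. Nor is the binary satisfaction endpoint, which is defined by the response labels of Item 14.

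**Working it through.** **Inputs.** The limit, recode and formula come from SAP 5.1.2. The documents do not print the response codes, so these are assumptions: every item starts at 1; Items 12 and 13 run 1-5; Item 14 runs 1-7. The floor below needs only the first assumption.

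**The other TSQM domains on the codes their constants imply.**
- Effectiveness and convenience, three items coded 1-7: (3 - 3)/18 = 0 and (21 - 3)/18 = 1, so 0 to 100.
- Side effects, four items coded 1-5: (4 - 4)/16 = 0 and (20 - 4)/16 = 1, so 0 to 100.

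**Overall satisfaction as printed.** Let R = 5/6 × (Item 14 - 1), so R runs from 0 to 5.
- Lowest set (1,1,1): (1 + 1 + 0 - 3)/12 × 100 = -8.33.
- Next set (1,1,2): (1 + 1 + 0.833 - 3)/12 × 100 = -1.39.
- Highest set (5,5,7): (5 + 5 + 5 - 3)/12 × 100 = 100.

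Of the 5 × 5 × 7 = 175 response sets, these first two are the only negative ones. The raw sum runs from 2 to 15, a span of 13, but the divisor is 12.

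**Do other codings repair it?**
- Items 12 and 13 from 0: floor -25.0. Item 14 from 0: floor -15.28. All three from 0: floor -31.94.
- Items 12 and 13 coded 1-4, 1-6 or 1-7: floor still -8.33, maximum 83.3, 116.7 or 133.3.
- Item 14 left unrecoded: (5,5,7) gives (17 - 3)/12 × 100 = 116.7, so the upper limit fails instead.
- With non-negative integer codes, a floor of exactly 0 requires Item 14 to start at 1 and the lowest codes of Items 12 and 13 to sum to 3, which makes them unequal. Nothing in the documents suggests this.

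**Forms that give exactly 0 to 100 on the assumed codes.**

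| Form | Points per step, Items 12 and 13 | Points per step, Item 14 | Share of Item 14 in total span |
|---|---|---|---|
| As printed | 8.33 | 6.94 | 5/13 = 38.5% |
| (a) Item 14 recoded as 1 + (Item 14 - 1) × 4/6; -3, /12 | 8.33 | 5.56 | 4/12 = 33.3% |
| (b) Printed recode; -2, /13 | 7.69 | 6.41 | 5/13 = 38.5% |
| (c) Item 14 unrecoded; -3, /14 | 7.14 | 7.14 | 6/14 = 42.9% |

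**Effect on change from baseline.** The constant cancels in a difference; the points per step do not.
- (2,2,3) to (4,4,6), half the range on every item: printed formula (2 + 2 + 2.5)/12 × 100 = 54.2. Forms (a), (b) and (c) all give 50.0. The ratio is 13/12 = 1.083.
- (2,2,4) to (4,4,3), Item 14 moving the other way: printed formula (2 + 2 - 0.833)/12 × 100 = 26.4. Forms (a), (b) and (c) give 27.8, 24.4 and 21.4.

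**The case against.** The best reply is that this shows two incompatible statements without showing which is wrong. If the instrument's scoring key prints this formula, the scores follow the instrument and the range sentence is what needs changing. That stands as a limit on the conclusion: the documents do not contain the key, so a mis-scaled estimate is conditional on the 0 to 100 range being the intended one. Both the protocol and the SAP state that range, and either way the SAP text must change.

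A second reply is that the limit may be a bound to enforce, with scores below 0 set to 0. The SAP states no such step. On the assumed codes it would alter only 2 of 175 response sets, and the 54.2 in the example would stay 54.2. It is fair to add that the documents state no intended weight for Item 14, so the weighting alone does not prove an error. But a 13-point span over a divisor of 12 departs from the rescaling rule the SAP writes out for the MFIQ and from the pattern of the other three TSQM formulas.

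A third reply is that the effect is small. Negative scores need the lowest answers, and no document says how often these occur. The 8.3% applies only when items move in parallel. The p-value is nominal, and under form (b) it would not change, because the score is then a linear rescaling. All of this is correct. It limits the consequence but leaves the primary endpoint without a formula that meets the SAP's own limit.

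**Conclusion.** The concern holds. As written, the formula cannot be applied with every score kept within 0 to 100 unless the programmer adds a rule that the SAP does not contain. The floor of -8.33 rests only on items being coded from 1. The range of -8.33 to 100, the 2 negative sets in 175 and the 13/12 factor also rest on codes of 1-5, 1-5 and 1-7.

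If a linear 0 to 100 scale was intended, parallel changes are overstated by 8.3%. Other patterns may show no error or an error of either sign, depending on the intended form. No direction of bias in the reported mean can be claimed, because the documents give no score distribution. The matter must be settled because it defines the primary endpoint, although no formal test depends on it.

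**What to change.** Check the overall satisfaction formula against the scoring key for TSQM version 1.4 and correct whichever statement is wrong. State the response codes of Items 12 to 14 in SAP 5.1.2, and verify that the lowest and highest response sets give exactly 0 and 100. Forms (a), (b) and (c) all pass that test on the assumed codes but weight Item 14 differently, so the key must decide between them. If the key itself allows scores outside the range, say so and state how they are handled.

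Then re-derive the baseline, visit and worst post-baseline scores and rerun the analyses that use them. Record the change in the SAP or, if the database is already locked, in the clinical study report. SAP section 10 already does this for its other corrections: "These changes will also be documented in the clinical study report".

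The cost is one formula and one line of derivation code, with no new data. The reported mean change may move. If all items shift in parallel it becomes 7.7% smaller (12/13, for example 54.2 to 50.0); otherwise it can move either way.
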